10.4 Safety Analyses

Safety variables are AEs, blood laboratory evaluations, UPTs (as required), local tolerability assessments and vital signs.

Adverse events will be coded from the verbatim text into preferred term (PT) and primary system organ class (SOC) using the most current version of Medical Dictionary for Regulatory Activities (MedDRA). Treatment-emergent AEs will be summarized in the following tables: all reported AEs, all treatment-related AEs, all SAEs, and AEs leading to investigational product discontinuation. The number and percent of subjects reporting the AE at least once will be tabulated according to the highest severity reported.

Laboratory evaluations and UPTs parameters will be summarized.

Vital signs, including changes from baseline, will be summarized by descriptive statistical methods as previously described.

Local tolerability assessments will also be summarized similarly as the treatment related AEs.

10.5 Sample Size and Power Estimation

For the binary version of the primary endpoint, i.e. proportion of subjects achieving at least a 1-point improvement in HDSM-Ax from baseline to end of therapy, assume the true response rates

Page 48 of 65

to be 75% for each BBI-4000 arm and 50% for vehicle control (based on prior data). With 100 evaluable subjects at a 1:1 ratio for each pairwise comparison between a BBI-4000 arm and the vehicle arm, i.e. 50 evaluable subjects per arm, the power is approximately 0.87 for observing a response rate difference in favor of BBI-4000 at a 1-sided p<0.10 level. To limit the study-wide false positive rate to 0.10, a gate-keeping hierarchical testing algorithm will be employed. That is, the BBI-4000 15% group will be compared to the vehicle first, if the result is favorable with a 1-sided p<0.10, then the BBI-4000 10% group will be compared to vehicle. Similarly, if the BBI-4000 10 % is favorable with a 1-sided p<0.10, then the BBI-4000 5% group will be compared to vehicle.

For the continuous version of HDSM-Ax change from baseline to end of therapy, assume the true mean difference between each BBI-4000 arm and the vehicle arm to be 0.18, with a common standard deviation of 0.36, i.e. an effect size (mean difference/standard deviation) of 0.50. With 100 evaluable subjects at a 1:1 ratio for each pairwise comparison between a BBI-4000 arm and the vehicle arm, the power is approximately 0.89 for observing a difference in favor of BBI-4000 at a 1-sided p<0.10 level. Same as for the binary version of HDSM-Ax, the gate keeping hierarchical testing algorithm will be employed for the continuous data.

Assuming an approximate 10% non-evaluable rate for the ITT primary efficacy analyses, 220 randomized subjects are targeted for enrollment.

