The primary efficacy endpoint is the change from baseline to the end of therapy in the mean HDSM-Ax score. The primary efficacy endpoint will be analyzed both as a continuous measure and as a binary outcome. As a continuous measure, the HDSM-Ax change scores will be compared between treatment groups in pairwise fashion by an ANCOVA model adjusting for the baseline HDSM-Ax score. The analysis will be performed with no imputation of missing data. As a binary measure, i.e. achieving a ≥ 1 -point improvement or not from baseline to end of therapy, a binary logistic regression will be performed with treatment assignment and baseline HDSM-Ax score as independent variables in the model. Any subject without a definable 1-point improvement (e.g., missing data) between Baseline and End of Treatment will be considered a non-responder. P values will generally be regarded as descriptive and statistical significance will be assessed using a gate-keeping hierarchy as described in Section [7.4.6.5](#) for both the continuous measure and binary data analyses.

The null hypothesis to be tested for the continuous measure is as below:

$$H_0: \mu_A \geq \mu_P;$$

where μ_A and μ_P represent the true underlying mean change scores for Treatment A (active drug) and Treatment P (vehicle), respectively. The alternate hypothesis to be tested is that the true active treatment group mean change score is smaller than the true vehicle group mean change score:

$$H_1: \mu_A < \mu_P;$$

Tested in the logit scale, the null hypothesis for the dichotomous outcome is that the true proportion of subjects with a 1 point or more improvement is lower in the active treatment group:

$$H_0: P_A \leq P_P;$$

The alternate hypothesis to be tested is that the true proportion of subjects with a 1 point or more improvement is higher in the active treatment group:

$$H_1: P_A > P_P;$$

7.4.4.2 *Sensitivity Analysis by Mixed Effects Models*

As a method that is known to be robust to missing data, mixed model repeated measures (MMRM) analyses will also be performed for the primary efficacy endpoint using all available HDSM-Ax change from baseline data on study days 8, 15, 22, 29, 36, and end of therapy. As fixed effects, treatment (active treatment group or vehicle gel), baseline HDSM-Ax score and visit (included in the class statement as a class variable) and baseline*visit interactions will be

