7.4.6.5 Multiple Comparisons/Multiplicity

To limit the study-wide false positive rate to 0.10, a gate-keeping hierarchical testing algorithm will be employed to assess statistical significance regarding the primary analyses for the primary efficacy endpoint, i.e. ANCOVA analyses on change from baseline in HDSM-Ax score. The hierarchy is, the comparison between BBI-4000 15% group and vehicle group will be considered first, if the result is favorable with a 1-sided $p < 0.10$, then the comparison between BBI-4000 10% group and vehicle will be considered. Similarly, if the BBI-4000 10% group is favorable with a 1-sided $p < 0.10$, then comparison between BBI-4000 5% group and vehicle will be considered. The same gate keeping hierarchical testing algorithm will be employed for both the binary data analysis and the continuous measurement analysis.

The primary efficacy analysis will be performed on the mITT population; the PP population will be utilized for selected efficacy analyses. The PP population is described in Section [7.2](#).

7.4.6.6 *Active-Control Studies Intended to Show Equivalence*

This study does not include an active-control product and is not intended to demonstrate equivalence between any two drug products.

7.4.6.7 *Examination of Subgroups*

There are no planned analyses to assess efficacy results by subgroups.

7.5 **Safety Analysis**

Safety analysis will be carried out for the Safety Population, to include all subjects who receive at least one dose of study drug. Subjects who do not complete the study, for whatever reason, will have all available data up until the time of termination included in the analysis. For safety analysis presented by study visit, the baseline value will be defined as the last value reported prior to first study drug administration.

7.5.1 *Extent of Exposure*

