The study phase of each therapy/procedure will be determined programmatically based on start and end dates. A prior therapy/procedure is defined as any therapy/procedure occurring prior to the date of the first dose of study drug. A concomitant therapy/procedure is defined as any therapy/procedure occurring on or after the date of the first dose of study drug. A therapy/procedure may be defined as both prior and concomitant. If it cannot be determined whether a therapy/procedure occurred prior to the start of study drug dosing due to partial or missing, it will be considered a prior therapy/procedure. Likewise, if it cannot be determined whether a therapy/procedure occurred after the start of study drug dosing, it will be considered concomitant. Therapies and procedures will be reported in a subject listing, and identified as prior or concomitant, and as a therapy or a procedure.

7.6 **Determination of Sample Size**

For the binary version of the primary endpoint, i.e., proportion of subjects achieving at least a 1-point improvement in HDSM-Ax from baseline to end of therapy, the true response rates will be assumed to be 75% for each BBI-4000 arm and 50% for vehicle control (based on prior data). With 100 evaluable subjects at a 1:1 ratio for each pairwise comparison between a BBI-4000 arm and the vehicle arm, i.e., 50 evaluable subjects per arm, the power is approximately 0.87 for observing a response rate difference in favor of BBI-4000 at a 1-sided $p < 0.10$ level.

For the continuous version of HDSM-Ax change from baseline to end of therapy, the true mean difference between each BBI-4000 arm and the vehicle arm will be assumed to be 0.18, with a common standard deviation of 0.36, i.e., an effect size (mean difference/standard deviation) of

0.50. With 100 evaluable subjects at a 1:1 ratio for each pairwise comparison between a BBI-4000 arm and the vehicle arm, the power is approximately 0.89 for observing a difference in favor of BBI-4000 at a 1-sided $p < 0.10$ level.

Assuming an approximate 10% non-evaluable rate for the mITT primary efficacy analyses, 220 randomized subjects are targeted for enrollment.

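### Should the sample-size sections state the power to declare the 10% and 5% gels significant under the fixed testing order?

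*Protocol*

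**What the plan says.** Protocol 10.5 assumes response rates of 75% in every active arm and 50% on vehicle. For the continuous version it assumes a mean difference of 0.18 with SD 0.36. The basis is stated as "With 100 evaluable subjects at a 1:1 ratio for each pairwise comparison between a BBI-4000 arm and the vehicle arm", that is, 50 per arm. The binary result is "the power is approximately 0.87 for observing a response rate difference in favor of BBI-4000 at a 1-sided p<0.10 level"; the continuous result is "the power is approximately 0.89 for observing a difference in favor of BBI-4000 at a 1-sided p<0.10 level".

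The same section sets the testing order to hold the study-wide false positive rate at 0.10. The 15% gel is tested first, then the 10% gel if 15% passes, and finally "if the BBI-4000 10 % is favorable with a 1-sided p<0.10, then the BBI-4000 5% group will be compared to vehicle". The order applies to both versions of the endpoint.

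SAP 7.6 repeats the power figures ("the power is approximately 0.87 for observing a response rate difference in favor of BBI-4000 at a 1-sided" and so on) without mentioning the order. SAP 7.4.6.5 does give it, ending with "then comparison between BBI-4000 5% group and vehicle will be considered". SAP 7.4.4.1 adds: "P values will generally be regarded as descriptive and statistical significance will be assessed using a gate-keeping hierarchy as described in Section" 7.4.6.5.

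**The concern.** A dose-ranging trial with three active arms reports one power per endpoint version and applies it to each active arm. Under the fixed order, though, 10% needs two rejections and 5% needs three, so 0.87 and 0.89 are the power to declare significance for the 15% gel only. SAP 7.6 makes this easier to miss because it gives the figures with no sign that a sequence governs significance.

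What is at stake is interpretation. If the 5% gel is not declared significant, a reader working from 0.89 would put the chance of missing a truly effective dose at about 0.11. Under the planned procedure and the plan's own equal-effect assumption it is about 0.24. That reader would count the result against the lower dose more heavily than the design allows.

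**Working it through.** **Inputs (Protocol 10.5).** n = 50 evaluable per arm; one-sided alpha 0.10, so z = 1.2816; rates 0.75 and 0.50; difference 0.18, SD 0.36, effect size 0.18/0.36 = 0.50. Allocation is 1:1:1:1 with one vehicle arm shared by all three comparisons.

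**1. The stated continuous figure.** Expected test statistic = 0.50 / sqrt(2/50) = 2.5. Power = Φ(2.5 − 1.2816) = Φ(1.2184) = 0.888. The noncentral t with 98 degrees of freedom gives 0.886. The plan says 0.89.

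**2. The stated binary figure.** Pooled rate 0.625. Standard error under the null = sqrt(0.625 × 0.375 × 2/50) = 0.0968; under the alternative = sqrt((0.1875 + 0.25)/50) = 0.0935. With a continuity correction of 1/50, power = Φ((0.25 − 0.02 − 1.2816 × 0.0968)/0.0935) = 0.871. Without the correction it is 0.911. Exact enumeration of Fisher's test gives 0.864. The plan says 0.87, so it matches the corrected or Fisher calculation.

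**3. Continuous version under the fixed order.** The comparisons share the vehicle mean, so with equal arms the test statistics have correlation 0.5. The probability that the first k comparisons all pass is the integral of φ(b) × Φ(√2 × 1.2184 − b)^k over b:

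- k = 1 (15% declared): 0.888
- k = 2 (10% declared): 0.815
- k = 3 (5% declared): 0.760

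A simulation of 400,000 trials with two-sample t tests gives 0.886 / 0.811 / 0.757. Multiplying the pairwise powers as if independent would give 0.789 and 0.701, which is too low. Because vehicle is shared, once 15% has passed the chance that 10% passes is 0.815/0.888 = 0.92, and once both have passed the chance for 5% is 0.760/0.815 = 0.93.

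**4. Binary version under the fixed order.** For each possible vehicle count v, take the probability that an active arm rejects given v, raise it to the power k, and average over the binomial(50, 0.5) distribution of v.

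| Test | 15% | 10% | 5% |
|---|---|---|---|
| Fisher, or continuity-corrected z | 0.864 | 0.778 | 0.718 |
| Logistic Wald, no covariate | 0.903 | 0.838 | 0.789 |
| Uncorrected pooled z | 0.907 | 0.842 | 0.793 |

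A normal approximation to the continuity-corrected test, with correlation 0.25/(0.25 + 0.1875) = 0.571, gives 0.871 / 0.795 / 0.741. Its gap from the first row is one of calculation, not of test: enumerated exactly, the corrected z and Fisher tests have the same sequential power.

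**5. Size of the loss.** Against the single comparison, the 10% gel loses about 6.5 to 8.6 points (0.907 − 0.842; 0.864 − 0.778). The 5% gel loses about 11 to 15 (0.907 − 0.793; 0.864 − 0.718). On the continuous version the losses are 0.888 − 0.815 = 0.073 and 0.888 − 0.760 = 0.128.

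**6. Sensitivity to equal effects.** Protocol section 1 reports greater improvement at 15% than at the lower strengths in study CL-201, with the earlier formulation. Illustrative continuous effects, in SD units for 15% / 10% / 5%:

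- 0.6 / 0.5 / 0.4: sequential 0.956 / 0.862 / 0.700, single comparison 0.956 / 0.887 / 0.761
- 0.7 / 0.5 / 0.3: sequential 0.986 / 0.881 / 0.557, single comparison 0.986 / 0.888 / 0.585

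In the second case the order costs under 1 point at 10% and about 3 at 5%.

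**The case for a change.** The case for a change is respectable. The SAP calls p-values generally descriptive, yet the same sentence leaves statistical significance to the hierarchy. The hierarchy exists to control the study-wide error rate, and the study describes itself as confirmatory. A plan that claims that control could be expected to state power under it. Equal effects are the sponsor's own assumption, and on that assumption the chance of missing an effective 5% arm roughly doubles. The cost is two or three sentences.

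The arithmetic stands, and so does the observation that SAP 7.6 is silent on the order. The step from there to a needed change does not. Neither document presents 0.87 or 0.89 as the power to declare 10%, 5% or all three doses, and no sample-size target is tied to those events. Protocol 10.3 takes a one-sided p below 0.10 for an active arm as a sign to go further, without requiring every dose to succeed. The SAP shells for Tables 14.2.1.3 and 14.2.1.7 give p-values against vehicle for every dose whether or not the sequence has stopped, and 14.2.1.3 adds the adjusted difference with its 95% interval. A reader judging the 5% gel will have these to hand.

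The binary figure is also not fixed by the documents. The planned test is logistic regression adjusted for baseline score, and no baseline correlation is given. Under SAP 7.4.4.1 a subject without a definable improvement "between Baseline and End of Treatment will be considered a non-responder". Taking as an assumption 55 per arm with 10% missing in each, the rates become 0.9 × 75% = 67.5% and 0.9 × 50% = 45%. Power is then 0.877 / 0.799 / 0.742 (unadjusted logistic Wald) or 0.833 / 0.735 / 0.667 (Fisher). Any binary pair written into the plan would carry a choice of test and missing-data rule that the stated 0.87 does not settle.

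**Conclusion.** No change is needed. This is a detail left unstated, not an error. The two powers are correct for what they are said to measure, the testing order is disclosed in both documents, and following the plan as written gives the same sample size, tests, thresholds, error control and reported results whether or not the extra figures appear.

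For anyone interpreting the lower doses, the power to declare 10% and 5% significant is about 0.81 and 0.76 on the continuous version. On the binary version it runs from about 0.78 and 0.72 (Fisher or continuity-corrected) to 0.84 and 0.79 (uncorrected z or unadjusted logistic Wald). These figures assume the same effect at every dose, 50 evaluable subjects per arm, one shared vehicle arm and no gain from baseline adjustment. They do not apply the SAP's non-responder rule, which under the assumption above lowers the binary figures. If 15% has the larger effect, the order costs the lower doses less.

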11 STUDY ADMINISTRATION PROCEDURES

11.1 Subject Entry Procedures

11.1.1 Overview of Entry Procedures

Subjects with hyperhidrosis as defined by the criteria Sections 4.2 and 4.3 (inclusion/exclusion criteria) will be considered for entry into this study.

11.1.2 Informed Consent and Subject Privacy

The study will be discussed with the subject, and a subject wishing to participate must give informed consent prior to any study-related procedures or change in treatment. The subject must also give Authorization for Use and Release of Health and Research Study Information and other written documentation in accordance with the relevant country and local privacy requirements (where applicable) prior to any study-related procedures or change in treatment.

11.1.3 Method for Assignment to Study Product Groups

All subjects who have signed an ICF will receive a 5-digit subject number, this number will be composed of a 2-digit site number followed by a 3-digit sequentially assigned number stating at 001, at each site. For instance, the first subject from site 01 will have 01001 as their assigned subject number; the subsequent subject from this site will have 01002 as their assigned subject number; the subsequent subject from this site will have 02001 as their assigned subject number; the subsequent subject from this site will have 02002 as their assigned subject number. This number

will be unique to each subject and will be used to identify the subject throughout the study. This number is different from the randomization/kit number.

When subjects qualify for the study (determined by the investigator at the Rescreening Visit), they will be randomized to investigational product groups and will receive a randomization number. The kit carton and treatment plastic pumps have the randomization numbers displayed in their label.

The next eligible subject will be assigned the lowest available randomization number from the treatment kits available at the depot. In this manner, eligible subjects will be randomized to the investigational product sequence in accordance with the randomization schedule. The investigator will document the randomization/kit numbers in the source and on the CRF. The tear-off portion of the carton label from the outer carton (with blind-break panel) will be removed along the label perforation and placed into the study subject source file. In the event a subject is randomized at the Rescreening Visit but is not dispensed study medication (e.g. deemed ineligible at Baseline, withdraws consent, etc.) the randomization number will not be reassigned; the subject will be considered an early termination and the kit shall be placed in quarantine in the site's inventory.

Subjects will be randomized to receive BBI-4000 5%, or 10%, or, 15% gel, or vehicle (placebo) gel in a balanced ratio of 1:1:1:1.

11.2 Compliance with Protocol

At each post-baseline visit, the following activities will occur to ensure compliance with the protocol:

- Subjects will be asked if they have used the investigational product as instructed.
- Subjects will be asked if they experienced any problems dispensing the investigational product.
- Subjects will be asked if they used any products on their axillae (including antiperspirant/deodorant).
- Site staff will review concomitant medication use since the previous visit and determine if any concomitant medication use qualifies as a protocol deviation
- At Day 22 (Visit 8) and the End of Treatment Visit site staff will collect the dispensing container from the subject and record the weight of the container.

11.3 Study Termination

The study may be stopped at a study site at any time by the site investigator, after first notifying the Sponsor and discussing the reason(s) for stopping the study. Brickell Biotech may stop the study with appropriate notification.

Page 50 of 65

12 ADMINISTRATIVE ISSUES

12.1 Posting of Information on Clinicaltrials.gov

Study information from this protocol will be posted on clinicaltrials.gov before enrollment of subjects begins.

12.2 Protection of Human Subjects

12.2.1 Compliance with Informed Consent Regulations (US 21 CFR Part 50) and Relevant Country Regulations

Written informed consent is to be obtained from each subject prior to enrollment into the study. Subjects may be consented up to 56 days before baseline visit.

12.2.2 Compliance with IRB Regulations

This study is to be conducted in accordance with IRB regulations (US 21 CFR Part 56.103). The investigator must obtain approval from a properly constituted IRB prior to initiating the study and re-approval or review at least annually. Brickell Biotech is to be notified immediately if the responsible IRB has been disqualified or if proceedings leading to disqualification have begun. Copies of all IRB correspondence with the investigator will be provided to Brickell Biotech.

12.2.3 Compliance with Good Clinical Practice

This protocol is to be conducted in accordance with the applicable Good Clinical Practice (GCP) regulations and guidelines, e.g., the International Conference on Harmonisation (ICH) Guideline on GCP.

12.3 Changes to the Protocol

The investigator should not implement any deviation from or changes to the protocol without approval by Brickell Biotech and prior review and documented approval/favorable opinion from the IRB of a protocol amendment, except where necessary to eliminate immediate hazards to study subjects, or when the changes involve only logistical or administrative aspects of the study (e.g., change in monitors, change of telephone numbers).

12.4 Subject Confidentiality

A report of the results of this study may be published or sent to the appropriate health authorities in any country in which the investigational product may ultimately be marketed, but a subject's name will not be disclosed in these documents. A subject's name may be disclosed to the Sponsor of the study, Brickell Biotech, the governing health authorities, or the FDA if they inspect the study records. Appropriate precautions will be taken to maintain confidentiality of medical records and personal information.

Page 51 of 65

12.4.1 Subject Privacy

Written Authorization and other documentation in accordance with the relevant country and local privacy requirements (where applicable) is to be obtained from each subject prior to enrollment into the study, in accordance with the applicable privacy requirements (e.g., the Health Insurance Portability and Accountability Act Standards for Privacy of Individually Identifiable Health Information; HIPAA).

